### **3.2 Primary Study Endpoints**

- Rate of progression-free survival of ipilimumab and SABR in patients with oligometastatic melanoma as measured from the time of study enrollment until the first documented date of disease progression by mWHO criteria

### **3.3 Secondary Study Endpoints**

- Rate of progression-free survival of ipilimumab and SABR in patients with oligometastatic melanoma as measured from the time of study enrollment until the first documented date of disease progression by irRC criteria
- Frequency of grade 3 and grade 4 toxicities according to CTCAE (Common Toxicity Criteria for Adverse Events) version 4
- Frequency of objective response rate, defined as complete response + partial response, measured by CT using modified World Health Organization (mWHO) criteria
- Frequency of objective response rate, defined using irRC
- Rate of local failure, as measured from the time of study enrollment until the first documented date of failure within the irradiated field
- Rate of overall survival, as measured from the time of study enrollment until the time of death

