### **2.2 Secondary Objectives**

The secondary objectives of this study are as follows:

- To evaluate the 6-month progression-free survival of the combination of SABR and 3 mg/kg ipilimumab in patients with oligometastatic melanoma using irRC criteria
- To evaluate the tolerability and safety of the combination
- To evaluate the response rate based on mWHO & irRC criteria
- To evaluate the local control rate
- To evaluate the overall survival rate

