## **6.0 STUDY PROCEDURES**

### **6.1 Treatment overview**

We will evaluate the combination of ipilimumab and SABR in patients with oligometastatic melanoma in this phase II trial.

The study will consist of the following schedule: ipilimumab will be administered on week 1 at a dose of 3 mg/kg.

Subsequent cycles of ipilimumab will be given every three weeks (week 4, 7, & 10).

SABR will be delivered between the second and third doses of ipilimumab (week 5-6) using the following suggested schedules: 18 Gy x 3 to lung, 10 Gy x 5 to liver, 6 Gy x 6 to nodal stations, 12 Gy x 3 to adrenal, 18 Gy x 1 to bone, and 24 Gy x 1, 18 Gy x 1, 15 Gy x 1 to < 2.0 cm, 2.0-3.0 cm, and >3 cm brain metastases, respectively.

Duration of therapy: Patients will receive at least 12 weeks of therapy and will be observed for toxicity for 90 days after the last ipilimumab infusion. Patients will remain on study until evidence of progression or death. Patients who meet criteria for reinduction therapy remain on study and re-induction is recommended if the criteria in Section 3.1.3 are met.

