### 6.3.2 Fractionation, Total Dose and Radiation Therapy Planning

Megavoltage external beam photon radiation therapy will be used delivered by a linear accelerator generating 6 MV photons or in the case of SRS to the brain a Gamma Knife. A CT simulation or MR simulation will be used for radiation therapy planning. During simulation where appropriate a 4-D CT should be used to determine the motion of targeted metastases with respiration. Efforts to limit respiratory motion such as gated treatment, Active Breath Control systems, or abdominal compression should be used in order to minimize necessary GTV to ITV expansions.

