### 6.3.4 Dose Considerations

Lung SABR recommended doses: 18 Gy x 3 to peripheral lung masses, 10 Gy x 5 to central lung masses given 2 fractions per week

Liver SABR recommended doses: 10 Gy x 5 given 2-3 fractions per week

Nodal station SABR recommended doses: 6 Gy x 6 given 3 fractions per week

Adrenal SABR recommended doses: 12 Gy x 3,

Vertebral body SABR recommended doses: 16-18 Gy x 1 respecting normal tissue spinal cord constraints particularly no more than 10 Gy to 10% of cord volume

Brain parenchymal SABR recommended doses: 24 Gy x 1, 18 Gy x 1, 15 Gy x 1 to < 2.0 cm, 2.0-3.0 cm, and >3 cm brain metastases, respectively dosed to the 50-70% isodose line if using Gamma Knife SRS.

Fractionation: Treatment shall be given 2-3 days per week at the treating radiation oncologist's discretion.

Dose Homogeneity: The dose throughout the treatment volume will be within 10% of the prescribed dose. Wedges, compensation, and other methods of generating a uniform dose distribution are encouraged. IMRT can be used to shape dose around critical normal structures.

Isodose Plans: The isodose distribution for the composite plan shall be calculated. The prescription point and the outline of the tumor volume shall be shown.

Image guidance: Pre-treatment kilovoltage on board CT imaging will be done for localization, and shifts will be made as appropriate per the treating radiation oncologist.

Treatment Modification: Uninterrupted treatment is planned, and SABR fractions should occur during the period between the 2nd and 3rd doses of ipilimumab (generally weeks 5-6). SABR can be delayed at the physician's discretion if there is concern for overlapping toxicities with ipilimumab, but SABR should always be delivered between infusion 2 and infusion 3 of ipilimumab. The entire course of SABR should be delivered within the 3 week period between ipilimumab infusions, except in the case of a grade 3+ toxicity in the middle of the course of SABR. If a grade 3+ toxicity occurs during SABR which interrupts the delivery of SABR, then the final SABR fractions will be delivered after the toxicity returns to grade or lower with appropriate supportive care measures.

On Treatment Management: The patient will be examined at least once a week during the course of radiation therapy.

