#### **6.5 Visit Schedule**

##### **6.5.1 Pre-Study Clinical Laboratory Tests and Procedures**

Prior to study treatment each patient will have the following assessments.

Within 4 weeks of starting study treatment:

- Radiologic studies for baseline tumor measurements with CT or MRI scanning (PET/CT is optional)
- History and physical exam
- CBC
- CMP
- Thyroid function and ACTH
- Urinalysis
- Serum pregnancy test
- Blood collection for correlative endpoints

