## **6.10 Definition of Efficacy Assessments**

- Rate of progression-free survival of ipilimumab and SABR in patients with oligometastatic melanoma as measured from the time of study enrollment until the first documented date of disease progression by both mWHO and irRC criteria.
- Frequency of grade 3 and grade 4 toxicities according to CTCAE (Common Toxicity Criteria for Adverse Events) version 4
- Frequency of objective response rate, defined as complete response + partial response, measured by mWHO criteria based on radiographic response rate will be determined based on re-staging CT of the chest, abdomen and pelvis
- Frequency of objective response rate, defined using the immune related response criteria (irRC) based on radiographic response rate will be determined based on re-staging CT of the chest, abdomen and pelvis
- Rate of local failure, as measured from the time of study enrollment until the first documented date of failure within the irradiated field
- Rate of overall survival, as measured from the time of study enrollment until the time of death

Biopsy, clinical evidence and radiographic evidence are all acceptable and will be used to document progression.

Overall survival: will be calculated as the time from entry on the study until the time of death.

Re-staging imaging with contrast-enhanced CT or MRI of the chest, abdomen, and pelvis will be performed before treatment, prior to 3rd ipilimumab infusion, 4 weeks after the final ipilimumab infusion (week 14 if there are no interruptions), and every 3 months for the first 2 years, then every 6 months during years 2-5.

The first re-staging scans after the week 14 imaging will be done at the 6 months from enrollment time point so that the endpoint of 6 month progression-free survival can be assessed.

All patients that have been treated on protocol with SABR and ipilimumab will have re-staging imaging even if they were taken off of protocol for adverse events after the SABR. Patients who do not have SABR due to adverse events from the first 2 infusions of ipilimumab are not required to complete re-staging imaging.

Patients who meet the criteria for Complete Response or Partial Response will have a re-imaging 4-weeks later to confirm the response.

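### Local failure is timed from enrollment although no irradiated field exists until SABR, so a timed local control rate is biased upward, and growth before SABR may be misread as in-field failure

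*Combined protocol and SAP*

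**What the plan says.** Local control is a secondary objective; section 2.2 reads "To evaluate the local control rate". Section 3.3 turns it into "Rate of local failure, as measured from the time of study enrollment until the first documented date of failure within the irradiated field", and section 6.10 repeats that definition.

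SABR timing is set relative to ipilimumab. Section 6.1 states "SABR will be delivered between the second and third doses of ipilimumab (week 5-6) using the following suggested schedules". The binding rule in section 6.3.4 is that "SABR should always be delivered between infusion 2 and infusion 3 of ipilimumab"; sections 3.1.2 and 6.3.4 present weeks 5-6 as the usual timing, not a limit.

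On imaging, sections 6.2 and 6.5.1 allow the baseline scan up to 4 weeks before treatment starts. Section 6.10 and Appendix II place the next scans before infusion 3 and 4 weeks after infusion 4. Section 6.10.2 gives a different schedule, every 6 weeks on study. For SABR itself, section 6.3.2 says "A CT simulation or MR simulation will be used for radiation therapy planning", but does not link that scan to any endpoint.

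Section 7.2 uses patients who received ipilimumab and SABR as the denominator for the primary rate and says that the secondary endpoints are evaluated in the same subjects. It then describes no local control analysis. No section gives a criterion for in-field failure, a reference scan or a censoring rule for this endpoint.

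**The concern.** Enrollment is a natural origin for PFS and overall survival, whose events can occur from the first day. In-field failure cannot occur until there is a field. Among patients analysed because they received SABR, the time from enrollment to SABR is event-free by construction, and a rate read at a fixed time credits it as local control.

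The second problem concerns measurement. If the lesion is compared with the screening scan, growth in the weeks before SABR can look like failure of SABR. The protocol expects such growth in some patients: sections 1.5.3 and 6.10.3 (Response Endpoints) say that lesions may enlarge early on ipilimumab, and two infusions precede SABR.

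The two errors act in opposite directions, and nothing ensures that they cancel. At stake is the reading of a named secondary objective, not the primary 6-month PFS decision.

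**Working it through.** The plan states no target, precision or landmark time for local control, so there is no plan figure to reproduce for this endpoint. The calendar can be checked. With week w starting on day 7(w - 1) + 1, infusions in weeks 1, 4, 7 and 10 fall on days 1, 22, 43 and 64. Four weeks after infusion 4 is day 64 + 28 = 92, the start of week 14, which agrees with section 6.10.

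**Lead-in before a field exists, from first dose**
- Earliest in the binding window (day after infusion 2, day 23): 22 days, 3.1 weeks.
- Start of week 5 (day 29): 28 days, 4.0 weeks.
- End of week 6 (day 42): 41 days, 5.9 weeks.

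The gap from enrollment to first dose is not stated. If it is assumed to be 0 to 4 weeks, the total shift is about 3 to 10 weeks, and longer if ipilimumab is delayed.

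**Effect on a timed rate**

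Assume a constant failure hazard h after SABR. True control at T months from SABR is exp(-hT). Timed from enrollment with lead-in L, it reads exp(-h(T - L)). One month is 30.44 days.

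- Section 1.2.3 cites 88% local control at 18 months: h = -ln(0.88)/18 = 0.0071 per month.
- Assumed poorer case, 70% at 6 months: h = -ln(0.70)/6 = 0.0594 per month.

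| Shift L | 88% at 18 months reads as | Gain (points) | 70% at 6 months reads as | Gain (points) |
|---|---|---|---|---|
| 4 weeks | 88.6% | 0.6 | 73.9% | 3.9 |
| 6 weeks | 88.9% | 0.9 | 76.0% | 6.0 |
| 10 weeks | 89.5% | 1.5 | 80.3% | 10.3 |

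A crude proportion of patients with in-field failure does not involve the origin and does not change.

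**Gap from screening scan to SABR**

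The longest gap on the planned weeks is 28 + 28 = 56 days for SABR at the start of week 5, and 28 + 41 = 69 days (9.9 weeks) at the end of week 6. With a screening scan on day 1 and SABR on day 29 it is 28 days.

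To illustrate the size, let volume double every DT days. The two-diameter product then grows by the factor 2^((2/3) x t/DT).

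| Assumed DT | 28-day gap | 56-day gap | 69-day gap |
|---|---|---|---|
| 60 days | +24% | +54% | +70% |
| 120 days | +11% | +24% | +30% |
| 180 days | +8% | +16% | +19% |

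A 25% increase is reached before SABR if DT is below t x (2/3)/log2(1.25): 58 days for a 28-day gap, 116 for 56 days and 143 for 69 days. The 25% is borrowed from the mWHO progression rule, which applies to a sum over index lesions; the protocol does not apply it to single irradiated lesions. The table also assumes unchecked growth through two infusions.

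**Whether another scan supplies a pre-SABR reference**
- The pre-infusion-3 scan may fall before, during or after SABR. If done on day 43, it is 1 to 14 days after a SABR start in weeks 5-6. Five fractions at 2 per week (section 6.3.4, central lung) span about 15 days, so a course begun on day 29 ends on day 43.
- The 6-weekly schedule in section 6.10.2 falls within or at the end of the SABR window.
- The nadir rule in section 6.10.2 does not help a lesion that grew before SABR with no scan in between: its smallest recorded size is still the screening value.
- The planning CT or MR does precede SABR, but is not named as a reference.

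**The case against.** The strongest reply is that the event is failure in the irradiated field, which can only follow SABR. The endpoint therefore does concern control after SABR, and the clock only shifts. At the cited control level the shift is 0.6 to 1.5 points, small beside sampling error in 32 patients: an observed 28/32 has an exact 95% interval of 71% to 96%. This stands as to size. A reader might infer that the rate does not measure control after SABR, or can be neither interpreted nor compared; the documents do not support that. The shift is nevertheless a systematic error with a known direction, grows when control is poor, and costs almost nothing to remove.

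Second, a reader might infer that the screening scan is the only reference. The protocol says no such thing: it names no reference for local failure, section 6.10 accepts biopsy and clinical evidence of progression, and section 6.10.1 classes lesions in a previously irradiated area as non-measurable. This stands, and is why the point is put as a risk of misclassification. It also shows that the endpoint lacks a criterion.

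Third, a 4-week minimum lead-in might be inferred from weeks 5-6, but the binding window allows just over 3 weeks from first dose. It might also be inferred that the 88% figure has a different time origin; section 1.2.3 does not state its origin, and section 7 sets no local control benchmark.

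Finally, section 7.2 already largely restricts the analysis to irradiated patients. That is correct, and it is what makes the lead-in guaranteed for everyone analysed.

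**Conclusion.** The time origin is misaligned with the event. Any timed local control rate among irradiated patients is biased upward by the clock, by about 0.6 to 1.5 points for a 4 to 10 week shift at 88% control at 18 months and about 4 to 10 points if 6-month control were 70%. These figures rest on a constant hazard after SABR; the 10-week end also assumes up to 4 weeks from enrollment to first dose, and the 70% is an assumption. A crude proportion is not affected.

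Growth before SABR may also be misclassified as in-field failure, because the only response scan reliably before SABR can be up to 69 days old on the planned weeks and no reference is named. How often this would happen cannot be computed from the documents: the growth table depends on assumed doubling times and a borrowed threshold, and at a 28-day gap even a 60-day doubling time stays just under 25%.

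This should be corrected. It affects a secondary endpoint with no formal test and leaves the primary analysis untouched.

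**What to change.** In sections 3.3 and 6.10:
- Time local failure from the first SABR fraction, among patients and lesions that received SABR, and report control at stated times after SABR.
- State the per-lesion criterion for in-field failure and the censoring rule, including how death without local failure is handled.
- Record the size of each irradiated lesion on the planning CT or MR that section 6.3.2 already requires, and name it as the pre-SABR reference.
- Do not count the pre-infusion-3 scan alone as showing local failure, since it may precede, overlap or closely follow SABR.

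Add the corresponding local control analysis to section 7.2.

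The cost is wording and recorded diameters; no imaging is added and treatment is unchanged. The downside is that the planning scan may differ in technique from the contrast-enhanced follow-up scans, whereas section 6.10.2 asks for similar techniques at each assessment. Record the method for each lesion, and show results against the screening scan as a sensitivity analysis.

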### **3.4 Correlative/Exploratory Study Endpoints**

Blood and tissue samples will be collected for research purposes. Planned studies include exploration of certain gene mutations and serum markers as predictors of response to ipilimumab treatment. Proteomics expression patterns will be used to

determine if they are a prognostic/predictive marker for treatment response. Research lab studies will also evaluate if primary tumor cells and melanoma stem like cells can be isolated from the tissues using our in-house laboratory techniques. These cells may be transitioned to long-term cell lines for further research.

### Sample collection scheme

Blood and serum samples for correlative analysis will be collected pre-treatment, prior to ipilimumab infusions and after completion of the treatment portion of the trial. The various time points for blood draw are shown in red circles with timelines. Tissue samples will also be collected in the event that re-biopsy or surgical resection is clinically indicated.

The Week 6-7 blood draw illustrated above will take place prior to the 3rd ipilimumab infusion and is hereafter referred to as the “Week 7” blood draw.

Blood and serum markers: We propose to determine the expression levels of various seromic proteins and cell surface markers. The marker proposed includes:

#### **Blood markers:**

- Change in Absolute Lymphocyte count (ALC) and LDH.

#### **T cell markers:**

- Change in Immune regulation after Ipilumimab infusion by measuring CD152 (CTLA-4) and CD28 (Co-stimulatory signal) by FACS.
- Change in T cell activation markers CD3, CD4, CD8, HLA-DR, ICOS, C11b, CD69, CD137, CD154, CXCL16 by FACS.
- Change in T cell suppressor – Myeloid derived suppressor cells CD14 and HLA-DR.

- Change in T helper 17 (Th17) cells and related cytokines IL-17 and IL-22 by intracellular cytokine staining and FACS- Change in Regulatory T cells 'Tregs' CD4, CD25/LAP, and CD127 by FACS and IDO by mass spectrometer
- Change in B-7 family costimulatory molecules: CD80(B7-1), CD86(B7-2) by FACS.

### **Cytokine Markers:**

- Change in cytokine milieu as assessed by the Bioplex Assays using serum samples: Human 8-plex assay; IL-2, IL-4, IL-6, IL-8, IL-10, GM-CSF, IFN- $\gamma$ , TNF- $\alpha$  and Human Th17 cytokine panel; IL-1 $\beta$ , IL-4, IL-6, IL-10, IL-17A, IL-17F, IL-21, IL-22, IL-23, IL-25, IL-31, IL-33, IFN- $\gamma$ , sCD40L, TNF- $\alpha$ , IL-17A/F by ELISA or FACS.

**Tissue sections:** Genomic DNA from the tissue sections will be isolated along with matched blood samples and will be used for the following analysis;

- Ratio of effector and regulatory T cells "Teff/Treg" by correlating with the levels of FoxP3 and IDO by IHC and RT-QPCR respectively in tissues when available.
- Rate of mutation and correlation to outcomes of key melanoma genes BRAF, NRAS, KIT, CDKN2A, PIK3CA, PTEN, TP53, MEK, EGFR, Akt, using castPCR technique.
- The tissue microarray (TMAs) obtained after Dermatopathologist selected/ reviewed area will be used for fluorescence based Immunohistochemistry and the expression intensity of images will be scored using an automated system.
- Change in tumor antigens over time such as Melan-A, NY-ESO-1, MAGE, MART-1, gp-100, and tyrosinase. The co-localization and subcellular localization / abundance will also be determined. We will also include ELISA based assay to estimate the antibody required for neutralizing melanoma antigens in serum.

#### **4.0 SUBJECT SELECTION AND WITHDRAWAL CRITERIA**

For entry into the study, the following criteria **MUST** be met. Any exceptions from the protocol-specific selection criteria must be approved by the Principal Investigator and/or the Institutional Review Board (IRB) before enrollment.

Patients must have baseline evaluations performed prior to the first dose of study drug and must meet all inclusion and exclusion criteria. Results of all baseline evaluations will be reviewed by the Principal Investigator prior to enrollment, to verify that all inclusion and exclusion criteria have been satisfied. In addition, the patient must be thoroughly informed about all aspects of the study, including the study visit schedule and required evaluations and all regulatory requirements for informed consent. The written informed consent must be obtained from the patient prior to screening procedures being performed. The following criteria apply to all patients enrolled onto the study unless otherwise specified.

##### **4.1 Inclusion criteria**

- 1) Willing and able to give written informed consent.
- 2)  $\geq 18$  years of age
- 3) ECOG Performance Status 0-2 (see Appendix I)
- 4) Histologic diagnosis of melanoma with metastatic disease to a visceral organ (lung, liver, brain, adrenal, nodal station outside the regional lymph drainage of the primary, vertebral bodies)
- 5) 1-3 sites of metastatic disease able to be targeted by SABR
- 6) Required values for initial laboratory tests:

- WBC  $\geq 2000/\mu\text{L}$
- ANC  $\geq 1000/\mu\text{L}$
- Platelets  $\geq 75 \times 10^3/\mu\text{L}$
- Hemoglobin  $\geq 9 \text{ g/dL}$  ( $\geq 80 \text{ g/L}$ ; may be transfused)
- Creatinine  $\leq 2.0 \times \text{ULN}$
- AST/ALT  $\leq 2.5 \times \text{ULN}$  for patients without liver metastasis,  
 $\leq 5$  times for liver metastases
- Bilirubin  $\leq 2.0 \times \text{ULN}$ , (except patients with Gilbert's Syndrome, who must have a total bilirubin less than 3.0 mg/dL)
- No active or chronic infection with HIV, Hepatitis B, or Hepatitis C.
- Negative Pregnancy test at screening
- WOCBP must have a negative serum or urine pregnancy test (minimum sensitivity 25 IU/L or equivalent units of HCG) within 3 days before the start of ipilimumab.

7.) Women of childbearing potential (WOCBP) and male subjects of fathering potential must be using an adequate method of contraception to avoid pregnancy throughout the study and for up to 3 months after the last dose of investigational product, in such a manner that the risk of pregnancy is minimized.

WOCBP include any female who has experienced menarche and who has not undergone successful surgical sterilization (hysterectomy, bilateral tubal ligation, or bilateral oophorectomy) or is not post-menopausal. Post-menopause is defined as:

- Amenorrhea  $\geq$  12 consecutive months without another cause, or
- For women with irregular menstrual periods and taking hormone replacement therapy (HRT), a documented serum follicle stimulating hormone (FSH) level  $\geq$  35 mIU/mL.

Women who are using oral contraceptives, other hormonal contraceptives (vaginal products, skin patches, or implanted or injectable products), or mechanical products such as an intrauterine device or barrier methods (diaphragm, condoms, spermicides) to prevent pregnancy, or are practicing abstinence or where their partner is sterile (eg, vasectomy) should be considered to be of childbearing potential.

Men of fathering potential must be using an adequate method of contraception to avoid conception throughout the study [and for up to 3 months after the last dose of investigational product] in such a manner that the risk of pregnancy is minimized.

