### ***Liver Function Test (LFT) Assessments Required Before Administration of Ipilimumab***

Liver function tests (AST, ALT, T. bilirubin) will be evaluated for every subject prior to administration of ipilimumab. Blood samples must be collected and analyzed at local or central labs within 3 days prior to dosing. LFT results must be reviewed by the principal investigator (or designee) to meet dosing criteria specifications:  $\leq 2.5 \times \text{ULN}$  for AST, ALT and  $\leq 1.5 \times \text{ULN}$  for T. bilirubin unless liver metastases are present in which case LFT  $\leq 5 \times \text{ULN}$  for AST, ALT and T. bilirubin  $\leq 3.0 \times \text{ULN}$  prior to dosing.

If during the course of treatment abnormal LFT values are detected, the subject must be managed using the hepatotoxicity algorithm section of the ipilimumab Investigators.

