## **6.6 Study Procedures By Visit and Treatment Cycle**

Note that results of all safety laboratory tests (that is, all chemistry and all hematology results) must be obtained and reviewed before ipilimumab administration, as applicable. All laboratory results must be within the established range before ipilimumab is administered. All induction period laboratory samples must be collected within a window of up to 4 weeks before administration of ipilimumab. Laboratory evaluations using a local laboratory must be performed and the result examined by the investigator before administration of each dose of ipilimumab.

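### For patients without liver metastases, the entry limit for bilirubin is looser than the pre-dose limit, and only the entry limit has a Gilbert's exception, so the plan can enrol patients whom its own dosing rule blocks.

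*Combined protocol and SAP*

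**What the plan says.** **Entry (Section 4.1, criterion 6).** Bilirubin may be up to 2.0 x ULN, "except patients with Gilbert's Syndrome, who must have a total bilirubin less than 3.0 mg/dL". There is no separate bilirubin limit for patients with liver metastases. AST and ALT may be up to 2.5 x ULN, or up to 5 times with liver metastases.

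**Before ipilimumab (Section 5.5, Liver Function Test Assessments Required Before Administration of Ipilimumab).** AST, ALT and total bilirubin "will be evaluated for every subject prior to administration of ipilimumab". On timing: "Blood samples must be collected and analyzed at local or central labs within 3 days prior to dosing". The limits are 2.5 x ULN for AST and ALT and 1.5 x ULN "for T. bilirubin unless liver metastases are present in which case LFT" limits become 5 x ULN for AST and ALT and 3.0 x ULN for bilirubin. Gilbert's syndrome is not mentioned here or in any other dosing rule.

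**General laboratory rule (Section 6.6).** "All laboratory results must be within the established range before ipilimumab is administered". The section does not define that range.

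**Analysis set (Section 7.3).** The primary endpoint is analysed in enrolled subjects who received at least two ipilimumab doses and SABR. Section 6.3.4 places SABR between infusions 2 and 3.

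**The concern.** A pre-dose rule that covers every subject also covers the first infusion. If it is stricter than the entry criterion, the protocol accepts a baseline value and then forbids treatment at that same value. The Gilbert's case is the sharper one. The entry criterion makes deliberate room for these patients, the dosing rule makes none, and the elevation may still be there at the next check.

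A site with such a patient has two options. It can withhold ipilimumab, in which case the patient is enrolled, does not reach two doses plus SABR, and falls outside the primary analysis set. Or it can treat and breach a written hepatic limit, for a drug whose background section (1.5.2, Immune-related Hepatotoxicity) reports fatal hepatic failure. The protocol does not say which of its two rules gives way.

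The AST and ALT limits agree between the two sections, with and without liver metastases. That suggests the bilirubin difference is an oversight.

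**Working it through.** The plan gives no figure to reproduce here. The check compares the two sets of limits by subgroup.

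**Inputs.** Entry: at most 2.0 x ULN, or below 3.0 mg/dL with Gilbert's (Section 4.1). Pre-dose: at most 1.5 x ULN without liver metastases, at most 3.0 x ULN with them (Section 5.5). The documents give no ULN for bilirubin, so I assume 1.0 to 1.5 mg/dL.

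**Step 1. Comparison in multiples of ULN.**

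| Subgroup | Entry | Pre-dose | Passes entry, fails pre-dose |
|---|---|---|---|
| No liver metastases, no Gilbert's | ≤ 2.0 x ULN | ≤ 1.5 x ULN | > 1.5 to 2.0 x ULN |
| No liver metastases, Gilbert's | < 3.0 mg/dL | ≤ 1.5 x ULN | > 1.5 x ULN and < 3.0 mg/dL |
| Liver metastases, no Gilbert's | ≤ 2.0 x ULN | ≤ 3.0 x ULN | none |
| Liver metastases, Gilbert's | < 3.0 mg/dL | ≤ 3.0 x ULN | none if ULN ≥ 1.0 mg/dL |

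**Step 2. Conversion to mg/dL.**

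| Assumed ULN (mg/dL) | 1.5 x ULN | 2.0 x ULN | 3.0 x ULN | 3.0 mg/dL as a multiple of ULN |
|---|---|---|---|---|
| 1.0 | 1.5 | 2.0 | 3.0 | 3.0 / 1.0 = 3.0 |
| 1.2 | 1.8 | 2.4 | 3.6 | 3.0 / 1.2 = 2.5 |
| 1.5 | 2.25 | 3.0 | 4.5 | 3.0 / 1.5 = 2.0 |

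- Without liver metastases or Gilbert's, the conflict band runs from above 1.5 to 2.0 mg/dL at ULN 1.0, and from above 2.25 to 3.0 mg/dL at ULN 1.5.
- With Gilbert's and no liver metastases, it runs from above 1.5 mg/dL (ULN 1.0) or above 2.25 mg/dL (ULN 1.5) to just under 3.0 mg/dL. It closes only when 1.5 x ULN reaches 3.0 mg/dL, that is at a ULN of 3.0 / 1.5 = 2.0 mg/dL, which is outside the assumed range.
- With Gilbert's and liver metastases, the pre-dose ceiling is 3.0 to 4.5 mg/dL. Any value below 3.0 mg/dL passes, so there is no conflict.

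**Step 3. Is there a way out in the text?** Section 4.0 allows approved exceptions, but only to the selection criteria; the rule that blocks the patient is a dosing rule. The dose-skipping rules in Section 5.3 are built around adverse events on treatment. They do not address a first dose blocked by a baseline value that the protocol accepted. What can resolve the conflict is a change in the value itself: Section 6.2 allows baseline chemistry up to four weeks before treatment, while Section 5.5 wants liver tests within 3 days of dosing.

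**Step 4. Effect on the primary analysis.** An undosed patient is not counted in the 6-month PFS rate, because Section 7.2 takes those who received ipilimumab and SABR as the denominator. The rule of 8 or more successes in 32 evaluable patients has type I error 0.096 and power 0.918 at 15% versus 35%. It keeps these properties provided 32 evaluable patients are still reached.

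**The case against.** The best defence is that the stricter rule is the dosing rule, so the protocol errs towards withholding drug and harm would require a further deviation. Investigators review baseline results before enrolment and liver tests before each dose, so the mismatch would be noticed. This is fair, and it limits the safety consequence. It does not tell the site which rule to follow, and it does not keep the patient in the analysis set.

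Four stronger readings are tempting, and the documents do not support them.

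- *These patients can never be dosed.* A reader might infer this, but a value of 1.5 to 2.0 x ULN at screening can fall to the limit by the pre-dose sample. Repeated failure is plausible only for a persistent elevation, as may occur with Gilbert's.
- *The limits contradict each other in both directions.* With liver metastases, entry stops at 2.0 x ULN and dosing at 3.0 x ULN. Because Section 5.5 governs every dose, a stricter entry limit can stand beside a looser limit on treatment. No enrolled patient is stranded, and Section 4.0 leaves a route to an entry exception. The two limits differ, where those for AST and ALT agree, but they do not contradict each other.
- *Section 6.6 sets a third limit.* Its established range can equally well mean the limits in Section 5.5. The wording is unclear, but it is not shown to conflict.
- *Each affected patient costs 3% of the trial (1 in 32).* Section 7.1 defines 32 as the number of evaluable patients, and an undosed patient is not one of them. The Study Summary and Section 7.4 are looser, giving 32 subjects and a planned enrolment of 32, but that does not turn 3% into a loss from the primary analysis.

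**Conclusion.** The point holds for patients without liver metastases and no further. In that group Section 4.1 admits bilirubin values that Section 5.5 does not allow at dosing: above 1.5 up to 2.0 x ULN in general, and above 1.5 x ULN up to just under 3.0 mg/dL with Gilbert's syndrome. The first band follows from the text alone. The Gilbert's band needs an assumed ULN and is present throughout 1.0 to 1.5 mg/dL.

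The consequence is a patient who is enrolled but outside the primary analysis set, or one who is dosed against a stated hepatic limit. The documents give no bilirubin distribution and no count of Gilbert's patients, so the number affected cannot be estimated. It is probably small and could be zero. The error rates of the primary test are not in question. This is an inconsistency between two written rules and should be corrected because one of them is a hepatic safety limit.

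**What to change.** The sponsor and investigator should reconcile Section 4.1 (criterion 6) with the liver function rule in Section 5.5 for patients without liver metastases, and state explicitly whether the Gilbert's exception applies to dosing. Section 6.6 should say which limits its established range refers to. While editing, they may wish to confirm that the difference between the entry and pre-dose bilirubin limits for patients with liver metastases is intended. Which limits are right is a clinical decision for them, and this review takes no position on it.

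The cost is an amendment to protocol wording, with no added tests or visits and no change to the sample size or decision rule. Depending on what is decided, the set of patients who can be enrolled or dosed may narrow or widen; the documents do not allow that to be quantified.
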